## **(MATE) Metformin and Aging Trial in the Elderly: A Pilot and Feasibility Study**

**Abstract.** Metformin exerts its effect on health span as a calorie restriction-mimetic through activation of AMP-activated protein kinase. This drug is safe, inhibits cellular senescence, and prolongs life in mammals. We hypothesize that chronic metformin administration through augmentation of cellular regeneration and inhibition of senescence improves physical functioning of older adults. In this pilot, feasibility study, we aim to administer metformin up to 2 gm or placebo in a 1:1 randomized fashion for one year to 12 frail adults,  $\geq 60$  years with coronary artery disease and assess their physical function by frailty measures. Among patients with improved physical function throughput profiling of tissue and serological samples will be made to establish a molecular map of the impact of metformin. The effect of metformin on several senescent markers (IL-6, MCP-1, MMP-3/9/12, PAI-1/2, and activin A) will be tested as well.

Version: 4

Date: October 5, 2020

**Principal Investigator: [name], MPH**

**A. Rationale:** Heart disease is the number one cause of death in the United States and disproportionately affects older adults, underscoring the need to examine determinants of survivorship. Recognizing this gap, ACC/AHA guidelines lay emphasis to assess frailty, a key construct prevalent in elderly and known to impact their prognosis. Older persons are commonly frail, and their health span is truncated by illnesses during which physiological declines together with accumulation of additional deficits results in multimorbidity and functional dependence. High incidence of functional decline in patients with coronary artery disease (CAD) makes pharmacologic manipulation, an attractive strategy to improve frailty and reduce adverse cardiovascular outcomes. Metformin exerts its effect on health span as a calorie restriction-mimetic through inhibition of mitochondrial complex 1 and activation of AMP-activated protein kinase. This drug is safe and has been shown to prolong life in mammals. Metformin by reducing effects of cellular senescence may improve the functioning of older adults.

In CAD, cellular senescence and inflammation affect organ dysfunction through interference with tissue homeostasis and regeneration. The deleterious effect of senescence includes pro-inflammatory senescence-associated secretory phenotype (SASP). Normal biological function through alteration in cellular homeostasis may be achieved by metformin. The phenotypic manifestations of these changes are incompletely characterized as it is yet unknown whether cell-intrinsic regenerative mechanisms can be translated into clinical improvement in physical performance and whether its chronic administration is safe in older adults. These major gaps in knowledge hinder utilization of metformin as an agent to promote cellular regeneration and to reduce the impact of cellular senescence.

Targeting frail individuals with high levels of inflammation and SASP factors would necessitate identification of predictors of improvement with metformin in tissue inflammation and function. A clinomics approach implementing simultaneous assessment of clinical impact coupled with OMICs-based serological profiling would provide enhanced understanding of the local and systemic impact mediated by metformin. Through correlation of molecular profiles with phenotypic expression changes, as proposed herein, we will enhance our understanding of the regenerative impact of metformin and the basis for clinical improvement in the setting of senescence.

[figure not shown]
**B. Hypothesis:** Chronic metformin administration through augmentation of cellular regeneration and reduction of senescence will improve frailty and physical functioning.

**C. Innovation:** This would be first-in-human pilot safety and feasibility study. There are no studies that have investigated the anti-aging potential of metformin.

**D. Significance:** 1. If proven, metformin will be given to improve physical functioning patients with CAD. Larger phase 3 studies would be needed. 2. This will enhance the reputation of Mayo Clinic, attract unique patients, and advance our knowledge about cardiovascular disease. 3. Increase in AMPK activity by metformin mimics calorie restriction by upregulating macroautophagy, mitochondrial biogenesis, inhibiting mTOR-1 allows cells to be functionally fit. TOR complex 1 can be successfully inhibited by metformin to slow senescence and improve human health. Metformin also inhibits cellular senescence, a key mammalian longevity pathway. Metformin extends lifespan in nematodes and mammals. It is safe and prevents progression from impaired glucose tolerance to clinical diabetes. Metformin among diabetics reduces risk of cardiovascular disease further supporting its role in attenuating age-related chronic diseases. Role of metformin as a pharmaceutical intervention to prevent aging is not derived from prospective studies. Cellular senescence arrests cells at risk for malignant transformation, however, the harmful effects may

manifest through their proinflammatory SASP. The role of metformin in modifying SASP is less well known, it is known to reduce senescence through prevention of translocation of NF- $\kappa$ B.

**E. Brief Synopsis of Methods:** 12 frail patients  $\geq 60$  years with CAD, will be randomized to metformin (up to 2.0 gm) or placebo for 1-year to note improvement in frailty. Molecular map through high throughput serological profiling and assessment of SASP will be done of responders and nonresponders to metformin. An IND exemption is being requested for the use of metformin.

**F. Preliminary data to support feasibility:** In a prospective cohort study, patients  $\geq 65$  years who underwent PCI were assessed for frailty (Fried criteria), comorbidity (Charlson index), and quality of life [SF-36]. Of the 628 patients discharged, 78 died. Following adjustment, frailty was associated with long-term mortality. In a recent pilot study, oral rapamycin (0.5, 1, 2.0 mg) was given for 12 weeks to 13 non-frail patients who underwent PCI. Plasma and adipose tissue markers of senescence were favorably modified by rapamycin [plasma IL-6 decreased from 4.4 to 2.6 pg/ml; adipose tissue mRNA expression of p16 (129 vs. 169), and senescence-associated beta galactosidase activity decreased (2.2% vs. 3.6%). Moderate correlation between some senescence markers and physical functioning was also demonstrated.

**Safety of metformin in nondiabetics:** The safety of metformin in patients without diabetes is well demonstrated in patients with diverse indications. In the Glycometabolic Intervention as Adjunct to Primary Coronary Intervention in ST-segment-elevation Myocardial Infarction (GIPS-III) randomized trial on 380 patients without diabetes mellitus, who received 1 gm of metformin for 4 months, no cases of lactic acidosis were observed. Importantly, the levels of creatinine, glucose, and HbA1C levels did not differ between the groups taking metformin or placebo underscoring the safety of the drug. Higher gastrointestinal side effects, which were self-limiting and did not require discontinuation of metformin were observed in patients with erectile dysfunction who also had insulin resistance as compared to placebo (61.5% vs. 7.7%, P=0.03). Similar results (higher gastrointestinal side effects) were seen with metformin in women with polycystic ovary syndrome (OR 4.49, 95% CI 1.88-10.72) or as an addition to chemotherapy in patients with advanced pancreatic cancer or when given to non-diabetic patients with coronary heart disease (CAMERA study) or with metformin pretreatment in patients undergoing coronary artery bypass surgery.

**G. Study design:** This will be a pilot, feasibility study. Twelve subjects  $\geq 60$  years with CAD, who are determined to be frail will be randomized to receive up to 2.0 gm of oral metformin or placebo for 12 months.

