**Molecular markers:** 50 mL of whole blood will be collected for omics assessment. EDTA tubes will be used by the CRTU staff to collect serological samples. The samples will be sent via pneumatic tube shuttle to the Hilton building for pick up by the [name] study team. Samples will be spun down, processed and/or stored for omics analysis. Study samples will be logged into the RLIMS system for sample management. Five randomly selected serological samples will undergo ELISA-based array evaluation to simultaneously quantify 1200 unique cytokines and growth factors. For non-stochastic evaluation, column-based immunodepletion will be utilized to eliminate albumin from five randomly selected samples prior to 2D-Gel separation and MS spectrometry-based deconvolution to establish the serum proteome. Serum samples will also undergo density filtration followed by rapid lyophilization or density concentration for isolation of the exosomal fraction. Purified serum exosomes will be enriched for small RNAs and subjected to miRNomics analysis. Data sets collected from this cohort will be cross-referenced with clinical frailty following chronic metformin treatment to document regenerative impact at the molecular level. This clinomics-based profiling will provide biomarker

readout to yield a systems-biology map of the mechanistic basis for regenerative benefit in those responsive to metformin therapy. The remaining samples will be stored for future use.

**Serum SASP markers:** will be measured at baseline, 3 months, and 12 months on all subjects. Serological markers of senescence will include [interlukin-6 (IL-6), matrix metalloproteinase (MMP) 3, 9, and 12, PAI-1 and -2, activin A, and monocyte chemotactic protein (MCP)].

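### The molecular map and the synopsis's SASP assessment contrast responders with nonresponders to metformin and name no placebo reference, so they can show correlates of improvement but not an effect of the drug

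*Protocol*

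**What the plan says.** The trial randomises 12 patients 1:1 to metformin or placebo (Abstract: "placebo in a 1:1 randomized fashion for one year to 12 frail adults"). Three places describe how the molecular data will be used.

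- **Section E (Brief Synopsis of Methods):** "Molecular map through high throughput serological profiling and assessment of SASP will be done of responders and nonresponders to metformin".
- **Abstract:** the profiled set is defined by outcome, "Among patients with improved physical function throughput profiling of tissue and serological samples", and this "will be made to establish a molecular map of the impact of metformin".
- **Section G, Molecular markers:** the omics data are linked to frailty after metformin treatment, to give a "systems-biology map of the mechanistic basis for regenerative benefit in those responsive to metformin therapy".

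None of these names placebo as the reference, and no responder is defined. Two other statements point the other way for SASP. The Abstract adds, apart from the map, that the effect of metformin on the senescence markers will be tested. The Serum SASP markers paragraph has them measured in every subject at baseline, 3 months and 12 months. For omics, the Schedule of Events collects blood without restriction by arm, but the cytokine array and the 2D-gel proteome are each run on five randomly selected samples only.

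**The concern.** A patient who improves on metformin has not thereby been shown to respond to metformin. Whether a patient improves is known only after randomisation, and a split on it within the active arm is no longer a randomised comparison. The protocol itself supplies other reasons for improvement:

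- Patients with an acute coronary syndrome or in cardiac rehabilitation are eligible (Definitions).
- The 3-month visit is timed to the end of rehabilitation (Schedule of Events).
- Entry is on the SPPB, so low scores at entry may drift back towards the patient's usual level.
- Exercise, diet, vitamin D and polypharmacy are listed as possible influences on frailty (Measurement of frailty).

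At stake is the mechanistic conclusion. Markers of rehabilitation, recovery or retest variation could be reported as the way metformin works and carried into the design of later studies.

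**Working it through.** The protocol gives no alpha, power or effect size (Section H disclaims power), so there is no figure to reproduce. The check is on the contrast; the numbers illustrate its size.

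**1. What the contrast identifies.** For a metformin patient, observed change = drug effect + change that would have occurred anyway + measurement error. Only the sum is seen. Splitting metformin patients on the sum and comparing markers shows what accompanies improvement from any source. Placebo patients show the last two terms without the first.

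If the Abstract's improved patients include both arms, the difficulty remains: placebo improvers would then contribute to a map labelled as metformin's impact.

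**2. Responders expected with no drug effect.** Inputs: 12 patients at 1:1, so 12/2 = 6 on metformin; p = probability of improving without drug, not given in the documents and assumed to be 10% to 50%. Expected number = 6p; chance of at least one = 1 − (1 − p)^6.

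| Assumed p | Expected responders of 6 | Chance of at least one |
|---|---|---|
| 0.10 | 0.6 | 0.47 |
| 0.20 | 1.2 | 0.74 |
| 0.30 | 1.8 | 0.88 |
| 0.40 | 2.4 | 0.95 |
| 0.50 | 3.0 | 0.98 |

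**3. If the drug does work.** Assuming it harms no one, the share of metformin improvers who would have improved anyway is (placebo rate)/(metformin rate). With assumed rates, 0.2/0.5 = 40%, 0.3/0.5 = 60% and 0.4/0.5 = 80%.

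**4. Information in each contrast, for assays run on all subjects only.** The smallest two-sided exact rank p is 2/C(n, k):

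- within metformin, 3 vs 3: 2/20 = 0.10
- within metformin, 2 vs 4: 2/15 = 0.13
- within metformin, 1 vs 5: 2/6 = 0.33
- randomised, 6 vs 6: 2/924 = 0.002

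**5. The five-sample assays.** Step 4 does not apply to them. Five samples split 3 vs 2 give at best 2/C(5, 2) = 2/10 = 0.20, whichever contrast is used. A change-from-baseline analysis in all 12 patients would need at least 12 × 2 = 24 samples; five hold at most two baseline and follow-up pairs. If the five came from five different patients (assumption), the hypergeometric probability of 2 or 3 being on metformin is 0.3788 + 0.3788 = 0.76, and of 0 or 1 it is 0.0076 + 0.1136 = 0.12. A random draw may therefore hold few or no metformin responders.

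**The case against.** The strongest reply is that the randomised comparison has not been given up. The Abstract says metformin's effect on the senescence markers will be tested, they are measured in both arms, and the Early withdrawal paragraph states intention-to-treat analysis. In a placebo-controlled trial the natural reading is a comparison between arms. This stands for SASP. A reader might infer from Section E that no placebo comparison of SASP is planned; the documents do not support that. What remains for SASP is a conflict between the synopsis and the other text. The intention-to-treat sentence concerns patients who stop the drug and does not say what the map compares.

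Second, the map is exploratory work in a 12-patient pilot, and its comparator could be left to a statistical analysis plan, which is not shown. A missing responder definition could indeed be left there. But the protocol itself states both the contrast and its causal reading, and a small sample does not justify that reading. Section A's aim of finding predictors of improvement with metformin also needs placebo patients, to separate prediction of drug benefit from prognosis.

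Third, improvement on placebo is not documented, and Section A cites frequent functional decline in coronary disease. This stands: placebo patients may improve, and the rates used here are assumptions.

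Fourth, the p-value bounds do not describe the array or the proteome, and no alpha is stated. This also stands. A reader might infer that moving to 6 vs 6 would make marker findings significant. For the array it would not: with 1200 analytes, 0.05/1200 is about 0.00004, well below 0.002.

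**Conclusion.** The point holds in a limited form. As written, the molecular map, and the SASP assessment as placed in Section E, rest on a contrast without a placebo reference and are then read as the impact and mechanism of metformin. That contrast can show correlates of improvement only. For SASP the text contradicts itself rather than omitting the randomised comparison.

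The size cannot be fixed from the documents. With an assumed 10% to 50% improving without drug, 0.6 to 3.0 of 6 metformin patients would be called responders under no drug effect. The bounds of 0.10 (3 vs 3) and 0.002 (6 vs 6) show the information lost only for assays run on all subjects; they are not a failure against any criterion the protocol sets. The harm is misattribution in an exploratory conclusion, not an error in a primary test.

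**What to change.** 1. In Section E, make the main SASP analysis the metformin-minus-placebo difference in change from baseline in all 12 randomised patients (6 vs 6). Do the same for any omics assay run on all subjects. This also brings Section E into line with the Abstract and the Serum SASP markers paragraph.
2. Relate marker change to SPPB change in both arms.
3. Keep responder and nonresponder displays as description, with the same definition applied to placebo patients. Remove the wording that attributes response to metformin, here and in Molecular markers ("mechanistic basis for regenerative benefit in those responsive to metformin therapy").
4. For the array and the 2D-gel proteome, draw the five samples from both arms and report them descriptively, without attribution to metformin.

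Cost: SASP is already measured in every subject, so the first three items need rewording and a little more analysis. Item 4 changes how the five samples are drawn, not how many, and the five-sample assays then support a weaker mechanistic claim. A full 12-patient change analysis on those two assays would need many more assays and is not proposed.

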If the patient agrees to participate in the study, the written informed consent will be obtained during the screening and baseline visit before any tests are performed. The consent process will occur in a private setting on the Mayo Clinic campus. The study team member will review the entire consent with the potential participant and answer any questions they may have about the research proposal. The potential participant will be provided as much time as needed to decide whether they want to participate or not. All potential participants will be assured that their clinical care will not be affected in any way if they choose not to participate.

**Definitions:** Coronary artery disease: Any patient with a diagnosis of CAD will be included. CAD will be defined as patients with history of angina, positive stress test, prior PCI or coronary artery bypass surgery or patients with significant coronary artery disease detected on CT scan. . Patients with known DM or new-onset DM will be excluded. Patients presenting with acute coronary syndrome or patients participating in cardiac rehabilitation will be eligible.

#### **Inclusion Criteria:**

- Age  $\geq$  60 years
- CAD
- Frailty as determined by the short physical performance battery
- Able to return for follow-up
- Written informed consent

#### **Exclusion criteria:**

- Pre-existing or new-onset diabetes
- Any active malignancy, hematological disorder, post organ transplant, immunocompromised
- Cancer requiring treatment in the past 3 years (other than non-melanoma skin cancer)
- Dementia [mini mental state examination (MMSE <20)]
- Prior stroke with disability
- Severe Parkinson's
- Hepatic insufficiency and/or chronic liver disease (cirrhosis)
- Chronic kidney disease (GFR < 45 mL/min)
- Taking metformin for any indication
- Acute alcohol intoxication
- Known hypersensitivity to metformin hydrochloride
- Acute/chronic metabolic acidosis, including diabetic ketoacidosis, with or without coma

**Measurement of frailty:** In prescreening patients via phone, we will ask 6 questions regarding ADLs and self-care to determine who will have a high likelihood of being frail. At the screening visit we will use the short physical performance battery (SPPB; Appendix 2) for identification of eligible participants. We will also measure frailty using the SPPB and grip strength at baseline, 3 months, and at the end of the study. Single-item frailty measures, such as gait speed, grip strength and repeated chair stands (if the participant is able to do), have shown important prognostic value in patients with CAD and will be recorded. Factors that potentially influence frailty (regular exercise regimen, vitamin D supplementation, high protein or calorie-restricted diet, or polypharmacy) will be recorded at each follow-up visit.

**Administration of Metformin** The gastrointestinal intolerance (diarrhea, nausea, bloating etc.) is associated with higher dose initiation and rapid dose escalation. The pharmacist under the guidance of an endocrinologist will start metformin at a lower dose (500 mg twice a day with meals) and increase the dose at one-week interval to a maximum tolerable daily dose up to 1.0 gm twice a day, depending upon patient's tolerance. Since metformin does not stimulate insulin secretion, hypoglycemia is rarely observed. Randomization to drug or placebo will be done by the statistician to ensure blinding. Administration and monitoring of metformin/placebo will be done by the study coordinator under the supervision of an endocrinologist, who will not be involved in the routine care or follow-up of these patients. The drug will be stopped during hospitalization for repeat angiography, or any acute condition that can adversely affect renal function or can cause lactic acidosis (infection, dehydration etc.). The study medication (placebo or metformin) will be restarted following hospital discharge according to the current FDA recommendations. Renal function will be monitored as a part of their clinical care on follow-up. The drug will be discontinued in patients reporting significant adverse effects.

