**I. Human study issues:**

**Human Subjects Safety:** An independent, internal data and safety monitoring board (DSMB) will oversee the progress and safety of the trial and will advise the investigators whether to continue, modify, or terminate the trial. Potential risks to participants may include side effects from metformin.

Protection of patient's identity will follow the Department guidelines for handling and storage of research data. Standardized systems to ensure patient confidentiality will be maintained.

Medication safety will be ensured by not giving metformin to anyone who has history of hypersensitivity to metformin or who have moderate-to-severe renal impairment (GFR<45mL/min/1.73m^2). Participants on metformin will discontinue the drug to prevent lactic acidosis if they will have a radiologic study with contrast, surgery, excessive alcohol intake, or any other precipitating factors. The only other serious adverse effect of hepatitis will be periodically monitored by blood tests, including serum bilirubin, ALT and AST.

**Early withdrawal of Subjects:** Participants with serious adverse effects from the medications will discontinue medication use, but will continue with the study visits, unless they wish to completely withdraw from the study. We will make arrangements for the participant to be seen by their primary MD for follow-up. At any other time, patients will contact the main study coordinator, if they develop and want to report any side effects. We will also discontinue medication use if the participants fail to follow the protocol or are unwilling to continue the prescribed medication.

Patients who discontinue the drug will come for their final check-up and will include frailty assessment, and blood draw for biomarkers. We would use intention-to-treat analyses and would not add any other subjects. The subjects who discontinue the study drug will be followed-up by a phone call at one month. If the discontinuation is due to serious adverse effect, the patient will be asked to contact the primary care provider and further management will be instituted.

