The reported incidence of lactic acidosis in patients receiving metformin hydrochloride is very low (approximately 0.03 cases/1000 patient-years, with approximately 0.015 fatal cases/1000 patient-years). In more than 20,000 patient-years exposure to metformin in clinical trials, there were no reports of lactic acidosis. Reported cases have occurred primarily in diabetic patients with significant renal insufficiency, including both intrinsic renal disease and renal hypoperfusion, often in the setting of multiple concomitant medical/surgical problems and multiple concomitant medications. Patients with congestive heart failure requiring pharmacologic management, in particular those with unstable or acute congestive heart failure who are at risk of hypoperfusion and hypoxemia, are at increased risk of lactic acidosis. The risk of lactic acidosis increases with the degree of renal dysfunction and the patient's age. The risk of lactic acidosis may, therefore, be significantly decreased by regular monitoring of renal function in patients taking Metformin and by use of the minimum effective dose of Metformin. In particular, treatment of the elderly should be accompanied by careful monitoring of renal function. Metformin treatment should not be initiated in patients  $\geq 80$  years of age unless measurement of creatinine clearance demonstrates that renal function is not reduced, as these patients are more susceptible to developing lactic acidosis. In addition, Metformin should be promptly withheld in the presence of any condition associated with hypoxemia, dehydration, or sepsis. Because impaired hepatic function may significantly limit the ability to clear lactate, Metformin should generally be avoided in patients with clinical or laboratory evidence of hepatic disease. Patients should be cautioned against excessive alcohol intake, either acute or chronic, when taking Metformin, since alcohol potentiates the effects of metformin hydrochloride on lactate

metabolism. In addition, Metformin should be temporarily discontinued prior to any intravascular radiocontrast study and for any surgical procedure.

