*Hypoxic states*—Cardiovascular collapse (shock) from whatever cause, acute congestive heart failure, acute myocardial infarction and other conditions characterized by hypoxemia have been associated with lactic acidosis and may also cause prerenal azotemia. When such events occur in patients on Metformin therapy, the drug should be promptly discontinued.

*Surgical procedures*—Metformin therapy should be temporarily suspended for any surgical procedure (except minor procedures not associated with restricted intake of food and fluids) and should not be restarted until the patient's oral intake has resumed and renal function has been evaluated as normal.

*Alcohol intake*—Alcohol is known to potentiate the effect of metformin on lactate metabolism. Patients, therefore, should be warned against excessive alcohol intake, acute or chronic, while receiving Metformin.

*Impaired hepatic function*—Since impaired hepatic function has been associated with some cases of lactic acidosis, Metformin should generally be avoided in patients with clinical or laboratory evidence of hepatic disease.

*Vitamin B12 levels*—In controlled clinical trials of metformin of 29 weeks duration, a decrease to subnormal levels of previously normal serum vitamin B12 levels, without clinical manifestations, was observed in approximately 7% of patients. Such decrease, possibly due to interference with B12 absorption from the B12-intrinsic factor complex, is, however, very rarely associated with anemia and appears to be rapidly reversible with discontinuation of metformin or vitamin B12 supplementation. Measurement of hematologic parameters on an annual basis is advised in patients on Metformin and any apparent abnormalities should be appropriately investigated and managed.

Certain individuals (those with inadequate vitamin B12 or calcium intake or absorption) appear to be predisposed to developing subnormal vitamin B12 levels. In these patients, routine serum vitamin B12 measurements at two- to three-year intervals may be useful.

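### The liver and alcohol entry criteria are narrower than the protocol's own safety text, and the baseline liver tests have no stated review before the first dose

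*Protocol*

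**What the plan says.** **Entry.** The Protocol's Exclusion criteria list "Acute alcohol intoxication" and "Hepatic insufficiency and/or chronic liver disease (cirrhosis". They contain nothing on habitual alcohol excess and no limit for AST, ALT or bilirubin. Other criteria in the same list do carry numerical limits: GFR below 45 mL/min and MMSE below 20.

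**Appendix 1.** The labelling text reproduced there is broader. On the liver, both Warnings and Precautions cover laboratory as well as clinical evidence: "Metformin should generally be avoided in patients with clinical or laboratory evidence of hepatic disease". On alcohol, Warnings says "Patients should be cautioned against excessive alcohol intake, either acute or chronic, when taking Metformin", and Precautions says that patients "should be warned against excessive alcohol intake, acute or chronic, while receiving Metformin". Neither chronic alcohol excess nor liver disease is among the listed contraindications.

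**Timing.** In the Schedule of Events, AST, ALT and bilirubin first appear in the baseline column, which also holds randomisation. The screening column has none of them.

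**On-treatment safety.** Section I, Human Subjects Safety, describes medication safety as "not giving metformin to anyone who has history of hypersensitivity to metformin or who have moderate-to-severe renal impairment", by the same GFR limit. It then takes participants off metformin for excessive alcohol intake, among other precipitants of lactic acidosis, and uses bilirubin, ALT and AST for periodic monitoring. Under Early withdrawal of Subjects, nobody who stops the drug is replaced.

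**The concern.** The people the entry list lets in are not the same as the people the safety text would want on the drug. There are two gaps.

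- **Liver (the stronger part).** A patient whose baseline AST, ALT or bilirubin is abnormal, but who is not judged to have hepatic insufficiency or chronic liver disease, passes the criteria. The result may come back after randomisation, and the protocol does not say who looks at it or what follows.
- **Alcohol (secondary).** A patient known to drink heavily, but not intoxicated at the visit, passes entry and then meets a condition for coming off drug.

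Appendix 1 gives a lactate mechanism for both. It says that alcohol potentiates metformin's effect on lactate metabolism. Its reason for the liver advice begins "Because impaired hepatic function may significantly limit the ability to clear lactate". The participants are older and frail with coronary disease, and the planned dose reaches 2.0 g a day for 12 months. Apart from the safety question, a 12-patient trial without replacement loses a visible share of its treated arm whenever one participant has to stop.

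**Working it through.** The protocol states no figure on this point, so there is none to reproduce. The check sets the rules side by side and then sizes what follows from them.

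**1. Liver rules compared**
- Entry: hepatic insufficiency, chronic liver disease. No laboratory limit.
- Appendix 1: avoid in general if there is clinical or laboratory evidence of liver disease.
- Schedule of Events: first liver tests at the randomisation visit.
- Human Subjects Safety: liver tests used for periodic monitoring, with no action level.

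The laboratory part of the Appendix 1 advice has no counterpart among the entry criteria, and no step links the baseline result to the first dose.

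**2. Alcohol rules compared**
- Entry: acute intoxication only.
- Appendix 1: caution the patient about acute or chronic excess.
- Human Subjects Safety: excessive intake takes a participant off metformin.

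The last rule applies to people already on drug, so it screens nobody at entry. A known heavy drinker satisfies the first rule and triggers the third.

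**3. Time to the next liver test, if an abnormal baseline result prompts nothing**

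Inputs: 3-month visit, window of ± 2 weeks (Study visits). Taking 3 months as 13 weeks, 13 − 2 = 11 and 13 + 2 = 15, so the next scheduled test falls about 11 to 15 weeks in. Administration of Metformin starts at 500 mg twice a day and allows increases at one-week intervals up to 1.0 g twice a day, so the full dose can be reached well before then. This interval is conditional: the protocol does not say when the first dose falls relative to the baseline results.

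**4. Expected lactic acidosis**

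Inputs: 12 patients randomised 1:1, so 12 ÷ 2 = 6 on metformin for one year, or 6 patient-years; rate "approximately 0.03 cases/1000 patient-years" (Appendix 1, Warnings).
- Metformin arm: 6 × 0.03/1000 = 0.00018 cases.
- One patient for one year: 1 × 0.03/1000 = 0.00003 cases.
- The documents give no rate for patients with alcohol excess or abnormal liver tests. If it were 10 to 100 times the overall rate (an assumption), one such patient treated for a year gives 0.00003 × 10 = 0.0003 to 0.00003 × 100 = 0.003 cases.

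**5. Loss of treated participants**

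One metformin participant taken off drug is 1/6 ≈ 17% of that arm, with no replacement. The documents give no prevalence for either condition, so no probability of enrolling such a patient is claimed.

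**The case against.** The case against is substantial, and much of it stands.

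- **No breach of the label.** A reader might infer that the entry list contradicts Appendix 1. It does not. On alcohol, the appendix asks only that patients be warned, and alcohol is not a listed contraindication. The entry list already goes beyond those contraindications by excluding acute intoxication and liver disease. Consent pages are not available here, so whether participants are warned there cannot be judged.
- **Hepatic insufficiency is undefined.** A reader might infer that only a recorded liver diagnosis excludes a patient. The wording does not require one, and an investigator could apply it on laboratory findings. The decision is then discretionary, without a stated limit or time point, which is a narrower fault than a missing exclusion.
- **The medication-safety sentence is not exhaustive.** Naming hypersensitivity and renal impairment there does not cancel the liver and alcohol exclusions elsewhere.
- **Heavy drinkers are not directed to a year at full dose.** A reader might infer this from the entry list alone. The on-treatment rule is not limited to single episodes, so a known heavy drinker would meet it. It may equally have been meant as a temporary hold, as for contrast studies and surgery, since the text does not say. On either reading it acts only after randomisation.
- **Other safeguards exist.** Appendix 1 is part of the protocol, an endocrinologist supervises dosing, and the drug is stopped for acute conditions that can cause lactic acidosis.

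These points reduce the finding's weight but do not remove it. None supplies a pre-dose review of the liver tests or aligns entry with the on-treatment alcohol rule.

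**Conclusion.** The point holds as a cheap improvement. The entry criteria are narrower than the safety text on which the protocol itself relies. The liver part is the firmer: Appendix 1 advises against dosing on laboratory evidence, the tests are already scheduled, and nothing states that they are read before the drug is given. The alcohol part is secondary: it is a mismatch between the entry and discontinuation rules.

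The size is small. Expected lactic acidosis is 0.00018 cases in the metformin arm at the quoted overall rate. It is at most 0.003 for one higher-risk patient under the assumed 100-fold multiplier. The practical loss, if such a patient is enrolled on metformin and must stop, is about 17% of that arm. No powered comparison is affected, because the trial is a pilot without one. The conclusion assumes six patients on metformin for a full year and that no unwritten review of baseline results takes place before dosing.

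**What to change.** 1. **Liver criterion (main change).** Extend the bullet to cover any other clinical or laboratory evidence of liver disease. Judge it on the baseline AST, ALT and bilirubin already in the schedule, against a limit set by the investigator and endocrinologist; the documents offer no figure for one.
2. **Timing.** State that these results are reviewed before the first dose, and preferably before randomisation, so that an ineligible patient does not use up one of the 12 places.
3. **Alcohol criterion (secondary).** Extend the bullet to current chronic excessive intake, with the intake limit named by the same two roles, and ask about it at screening. Entry then matches the on-treatment discontinuation rule.

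**Cost.** Two amended bullets, one sentence on timing and one history question, with no new test. The downside is a short wait for the liver results and possibly a few lost candidates.
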